## **Regional Nerve Blocks for Major Lower Extremity Amputations: Effects on Postoperative Pain Control and Length of Stay**

**Synopsis:** This study will analyze patients undergoing major lower extremity amputations by the vascular surgery service at UCSF Fresno to determine if regional nerve blocks (sciatic and femoral) have any effect on postoperative pain control, narcotic requirements, and length of stay compared with standard post-operative narcotic regimens.

**Hypothesis:** We hypothesize that patients undergoing major lower extremity amputations with regional nerve blocks have better postoperative pain control, decreased narcotic requirements, and shorter length of stay when compared with patients who receive post-operative narcotic pain medications only.

**Specific Aims:** To determine if regional nerve blocks provide better postoperative pain control, decreased length of stay, and decreased narcotic requirements for patients undergoing major lower extremity amputations.

**Background and Significance:** Major lower extremity amputations (above knee amputation or below knee amputation) are common procedures performed for patients with end stage ischemia, infection, and/or disfigurement. Patients undergoing major lower extremity amputations have significant morbidity and mortality. Up to 95% of amputees report chronic pain, and inadequate pre- and postoperative pain control may increase the risk of chronic amputation pain. Additionally, there is a growing epidemic of narcotic overdoses in the United States. From 2000 to 2014, the age-adjusted drug overdose death rate has more than doubled from 6.2 per 100,000 persons to 14.7 per 100,000. The main drugs associated with overdose deaths are prescription pain medications.

Regional nerve block is part of usual care and may serve as adjuncts for pain control after major lower extremity amputations. This pain control may be achieved by injecting bupivacaine into the sciatic and femoral nerves. Bupivacaine is an amide-type local anesthetic approved by the Food and Drug Administration (FDA) for local or regional anesthesia or analgesia for surgery. The dosage approved by the FDA for peripheral nerve blocks are 0.25% and 0.5%. The potential risks are central nervous system and cardiovascular system reactions. The central nervous system reactions are characterized by restlessness, anxiety, dizziness, or tremors. The cardiovascular system reactions are characterized by decreased cardiac output, heart block, hypotension, bradycardia, or arrhythmia. These risks are small and can be minimized further by slow administration and aspiration prior to administration to avoid intravascular injection. Other rare but potential risks of regional nerve block are nerve injury and hematoma formation.

Although bupivacaine is widely used for pain control, there are very few studies looking at regional nerve blocks as adjuncts for pain control after major lower extremity amputations. The number of randomized controlled trials is even fewer and none have been conducted in the United States. Baddoo looked at ten patients undergoing major lower extremity amputations (nine above knee amputations and one below knee amputation) with regional nerve blocks (a sciatic nerve block combined with either a 3-in-1 block or a psoas compartment lumbar plexus block). All ten patients were

### **Design of the study:**

#### Prospective enrollment:

This study was a double-blinded randomized controlled trial analyzing 40 patients undergoing major lower extremity amputation by the vascular surgery service at UCSF Fresno at Community Regional Medical Center, Clovis Community Medical Center, and Fresno Heart and Surgical Hospital. All included patients were evaluated by the vascular surgery service and had lower extremity amputation deemed necessary based on ischemic disease, infectious disease, and/or disfigurement. Patients were excluded if they were less than 18 years of age, pregnant, undergoing emergency amputations, staged amputations, or amputations by non-vascular surgeons, have known allergies to bupivacaine, are unable to communicate symptoms of pain, or refuse to participate in the study. Eligible patients were identified by the vascular surgery service in their private office or following a consultation by the vascular surgery service in the hospital. Upon identification, eligible patients or their surrogate decision maker were approached for consent by a member of the study team.

To randomize patients, consent forms were pre-labeled with a random subject identification number. This number served as the participants' study ID for all data collection in order to maintain privacy and confidentiality. Additionally, this number was linked to a sealed envelope containing the random treatment group. The study coordinator created the labels and assembled the envelopes to ensure all investigators remained blind to the treatment groups. This sealed envelope was given to the anesthesia providers, by the vascular surgery service, for the amputation. The anesthesia team then administered the assigned treatment prior to induction of general

anesthesia. Half of the patients were randomized into the treatment group, and half of the patients were randomized into the control group.

Patients randomized to the treatment group received regional nerve blocks (sciatic and femoral) with bupivacaine at the dose of 1 mg/kg. The anesthesiologists are experts in pain management, and they are trained to perform regional nerve blocks. Femoral and sciatic nerve blocks are within their scope of practice, and they have been performing them quite frequently especially in orthopedic operations. Patients randomized to the control group received two needle sticks (in the sciatic and femoral distributions) with normal saline to maintain the double-blinded investigation. Because the injections are the standard of care, the appropriate billing codes already exist in Epic electronic medical record and are regularly used by the anesthesiologists. Therefore, for this study, the anesthesiologists ordered and documented the injections as normal.

The remainder of the operation and post-operative course proceeded per the standard of care. Post-operative pain was evaluated daily until discharge by the vascular surgery service using the McGill pain questionnaire. Additional data collected included age, gender, race, BMI, ASA class, length of operation, hospital length of stay, oral and parenteral narcotic pain requirements. Any adverse events were immediately reported to the Principal Investigator and the IRB. A Medical Monitor with suitable expertise was provided with study data every 3 months. The medical monitor used that data, especially the unforeseen adverse events and complications, to ensure the study safety. The patients were monitored while in the hospital and after discharge. The patients followed up per routine in vascular office, and pain along with other data was collected until six months after discharge.

Enrollment for the prospective portion is now closed and all patients have been discharged.

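### The retrospective block versus no-block comparison is unadjusted and omits non-opioid analgesia and block timing, so its narcotic difference could be biased in either direction

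*Combined protocol and SAP*

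**What the plan says.** The Hypothesis sets block patients against others: "when compared with patients who receive post-operative narcotic pain medications only". The Synopsis words the comparator more loosely, as standard narcotic regimens after surgery.

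Under Design of the study, Prospective enrollment, pain is assessed daily with the McGill questionnaire. The protocol then says: "Additional data collected included age, gender, race, BMI, ASA class, length of operation, hospital length of stay, oral and parenteral narcotic pain requirements". Other care is not fixed: "The remainder of the operation and post-operative course proceeded per the standard of care". Background and Significance adds: "Regional nerve block is part of usual care and may serve as adjuncts for pain control after major lower extremity amputations".

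The Retrospective review section compares patients who had a block with those who did not on the same items, without a pain score. It does not say when a block must have been given to count. The Statistical Analysis section plans t-tests, Mann-Whitney tests and chi-square tests, with no adjusted model. The Sample Size section expects about 1000 patients, of whom 40 were randomized.

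**The concern.** Non-opioid analgesics can lower narcotic use by themselves. In the retrospective review nobody was randomized, so the choice of a block may go together with the choice of a non-opioid regimen. None of the patient or operative variables listed (age, gender, race, BMI, ASA class, length of operation) captures that second choice, and the planned tests adjust for nothing. The effect of accompanying drugs would then be credited to the block, or set against it.

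Two further gaps act on the same comparison. Opioids given by routes other than oral or parenteral are not counted. And because block timing is undefined, a patient blocked after surgery for uncontrolled pain could be placed in the block group, taking high narcotic use and a long stay into it.

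The stakes are highest here because the retrospective review supplies most of the patients. With no pain score on its list, narcotic requirement and length of stay are the only hypothesized outcomes it can address.

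**Working it through.** The plan has no figure of its own to reproduce: it gives no effect size, standard deviation, alpha, power or analgesic usage. What follows shows possible size under stated assumptions.

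**Share of patients affected.** Taking the 1000 to include the 40 randomized: 1000 - 40 = about 960 retrospective patients.

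**Apparent effect when the block does nothing.** Let r be the proportional cut in narcotic use from a non-opioid regimen, and pB and pN the shares of block and no-block patients who receive it. All three are assumed.

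Apparent reduction = 1 - (1 - r × pB)/(1 - r × pN)

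With pN = 0.4:
- r = 0.2, pB = 0.6: 1 - 0.88/0.92 = 4.3%
- r = 0.2, pB = 0.8: 1 - 0.84/0.92 = 8.7%
- r = 0.3, pB = 0.6: 1 - 0.82/0.88 = 6.8%
- r = 0.3, pB = 0.8: 1 - 0.76/0.88 = 13.6%

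Now reverse the imbalance, with pB = 0.4 and pN = 0.6 to 0.8. The ratio of block to no-block narcotic use is 0.92/0.88 = 1.045 at one end and 0.88/0.76 = 1.158 at the other. An ineffective block would appear to raise narcotic use by about 4.5-16%, and a real saving would be hidden by a similar amount. Nothing in the documents favors one direction.

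**Chance of a false positive.** Assume 500 against 500 (the real split is not given), two-sided alpha 0.05 and a normal approximation. The standard error of a standardized difference is √(2/500) = 0.063. Bias is the imbalance in use times the effect of the drugs in SD units:
- 0.1 × 0.3 = 0.03 SD: probability of a significant result about 8%
- 0.2 × 0.5 = 0.10 SD: about 35%
- 0.3 × 0.5 = 0.15 SD: about 66%
- 0.5 × 0.5 = 0.25 SD: about 98%

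With so many patients, even a small bias can produce a significant result from an ineffective block.

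**The randomized part, 20 against 20.** The protocol describes it thus: "This study was a double-blinded randomized controlled trial analyzing 40 patients undergoing major lower extremity amputation", and "Half of the patients were randomized into the treatment group, and half of the patients were randomized into the control group".
- Type I error: with 50% non-opioid use in both arms and a 0.8 SD effect of those drugs, 20,000 simulated trials gave 0.049. Leaving the drugs unmeasured does not inflate the error.
- Chance imbalance in use: 1.96 × √(2p(1 - p)/20) is ±0.28 for p = 0.3 or 0.7 and ±0.31 for p = 0.5. A single trial can therefore differ by some 30 percentage points.
- More non-opioid use in the saline arm: take a true difference of -0.80 SD and a 0.5 SD drug effect. Use of 70% against 40% gives -0.80 + 0.5 × 0.3 = -0.65 SD; 80% against 30% gives -0.80 + 0.5 × 0.5 = -0.55 SD. This shrinks the difference and creates no false benefit.

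**The case against.** A reader might infer that other analgesia went unrecorded. The documents do not support that. They say "the anesthesiologists ordered and documented the injections as normal", in Epic, and that in follow-up "pain along with other data was collected until six months after discharge". They show only that these items are not named study variables; the chart may well hold them.

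A reader might also infer that lower narcotic use in the randomized trial cannot be separated from other drugs or a later block. That too goes beyond the text. With random allocation and saline injections as control, the narcotic difference is a valid effect of assignment under usual care, and later differences in co-analgesia are part of its consequences. The anesthesia providers received the envelope, but nothing says that they managed pain on the ward or offered later blocks unequally.

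On the comparator, the word only in the Hypothesis can fairly be read, alongside the Synopsis, as without a block. It need not exclude non-opioids, so no breach of a stated comparator is claimed.

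Finally, every usage figure above is assumed, and unlisted co-analgesia is one instance of a wider weakness: a non-randomized comparison with no adjustment. Both points stand. They limit what can be said about size, but they do not remove the gap in the variable list or in the analysis.

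**Conclusion.** The point holds for the retrospective review. As written, the plan would attribute to the block any difference in accompanying non-opioid analgesia, in about 960 of roughly 1000 patients, and its variable list would not let a reader detect this. The direction is unknown. The illustrative size is a spurious reduction of about 4-14%, or a reversed bias of similar size that hides an effect; both rest wholly on the assumed 20-30% drug effect and the assumed usage shares. The effect on length of stay cannot be sized from the documents.

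For the randomized part this is a matter of reporting and interpretation. The comparison is valid; more rescue analgesia in the saline arm would dilute it.

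**What to change.** The review is written in the future tense, so the change can be made before extraction.

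**Retrospective review**
- Add to the Epic report: non-opioid analgesics, opioids by any route, and the date and time of every nerve block or epidural.
- Define the block group by a block given before or at surgery.
- Replace the unadjusted narcotic and length-of-stay comparisons with a regression that includes non-opioids ordered before or at surgery and the baseline variables already listed (age, gender, race, BMI, ASA class). Do not adjust for non-opioids started afterward, since these may be consequences of how well the block worked.

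**Randomized part**
- Keep patients as randomized and report non-opioid use and later blocks by arm. Recorded times will separate the study injection from a later block.
- State that the result is the effect of assignment under usual co-analgesia, and that more rescue in the saline arm would dilute it.
- Do not rank patients with a later block as the worst narcotic outcome. If such blocks were offered unequally, provider behavior would become an apparent benefit of the study block. With enrollment closed, the rule would also be post hoc.

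The cost is more extraction work and a regression model in place of two-group tests. Adjustment will not make the retrospective comparison equivalent to a randomized one, and the report should say so.

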#### Retrospective review:

In addition to the 40 patients prospectively enrolled and randomized, a retrospective review will be performed on all patients undergoing major lower limb amputation from July 2017 through December 2020. These patients will be identified through an Epic report with inclusion/exclusion criteria the same as the prospective portion, with the exception of refusal to participate as this portion will have a waiver of informed consent.

Patients with a regional nerve block will be compared to those without on age, gender, race, BMI, ASA class, length of operation, hospital length of stay, and oral and parenteral narcotic pain requirements.

**Statistical Analysis:** The two groups will be compared using descriptive statistics. Continuous data will be analyzed using student's t-test and/or Mann-Whitney U tests and categorical data will be analyzed using Chi square analysis.

**Sample Size:** We expect to include approximately 1000 patients in this study.

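### The 40-patient randomised comparison is planned with unadjusted tests only and lists no amputation level: a missed, possibly small, gain in precision and balance that a prespecified adjusted model could recover

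*Combined protocol and SAP*

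**What the plan says.** Under Prospective enrollment, the protocol states: "This study was a double-blinded randomized controlled trial analyzing 40 patients undergoing major lower extremity amputation". Allocation was equal: "Half of the patients were randomized into the treatment group, and half of the patients were randomized into the control group". The mechanism was a pre-assigned study number, and "this number was linked to a sealed envelope containing the random treatment group". No stratification factor or blocking is mentioned.

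The Background defines the population as "Major lower extremity amputations (above knee amputation or below knee amputation" procedures, and the eligibility criteria do not restrict level. It also says that "inadequate pre- and postoperative pain control may increase the risk of chronic amputation pain".

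The trial's data list reads: "Additional data collected included age, gender, race, BMI, ASA class, length of operation", followed by stay and narcotic use. The comparison list under Retrospective review names the same items. Neither list includes amputation level or preoperative opioid use. Pain is described as scored after surgery with the McGill questionnaire, and no preoperative score is listed.

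The Statistical Analysis paragraph offers t-tests and/or Mann-Whitney tests for continuous data and chi-square tests for categorical data. It has no regression, covariance adjustment or stratified analysis. It follows the retrospective section and speaks only of two groups. No separate analysis is given for the trial, so it applies to the trial by default.

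**The concern.** With 20 patients per arm and no stated stratification, the arms can differ noticeably by chance on a baseline factor. If level of amputation affects pain, narcotic use or stay, such a difference moves the estimated block effect up or down. An unadjusted test has no means of correcting for it. If level was not recorded, a reader of the results could not even see whether the arms were balanced.

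Baseline factors that predict outcome also carry precision that a two-sample test does not use. Enrolment is closed, so the randomised numbers cannot grow. Closure rules out stratified allocation and new baseline questionnaires. It does not rule out choosing a better model or reading one more item from the operative record.

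**Working it through.** **Inputs from the protocol.** 40 randomised, 1:1, so 20 per arm (Prospective enrollment). Alpha, sidedness, power, effect size and SD are not stated, so the 40 cannot be reproduced.

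**Assumptions.** Two-sided alpha 0.05, 80% power, outcome SD of 1, above-knee share 30% to 50%, and combined correlation r of the covariates with outcome of 0.3, 0.5 or 0.7. None of these comes from the documents.

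**1. Chance imbalance in level.** A gap of 20 points is 4 patients of 20.
- Each arm drawn as binomial(20, p), P(|X1 − X2| ≥ 4): 22.6% at p = 0.3 and 26.8% at p = 0.5.
- Total above-knee held fixed at 12 or 20 of 40 (hypergeometric): 30.1% and 34.3%.

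**2. What an imbalance does.** Suppose level shifts the outcome by 1 residual SD.
- A 30-point imbalance biases the unadjusted difference by 1 × 0.30 = 0.30 SD.
- With half the patients at each level, the unadjusted critical difference is about 1.96 × √(1 + 0.25) × √(2/20) = 0.693. The standard error given the imbalance is √(2/20) = 0.316.
- Conditional type I error: P(Z > (0.693 − 0.30)/0.316) + P(Z < (−0.693 − 0.30)/0.316) ≈ 0.11.
- At a 20-point imbalance the same calculation gives about 0.06.
- A 30-point gap has probability 6% to 8% (binomial) or 8% to 11% (total fixed). Averaged over all randomisations, the error rate stays at about 5%.

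**3. Unadjusted detectable difference.** (t0.975 + t0.80 on 38 df) × √(2/20) = (2.024 + 0.851) × 0.316 = 0.91 SD. Solving the noncentral t gives 0.909. Power for a true 0.8 SD difference is 69%.

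**4. Adjusted detectable difference.** Adjustment multiplies the variance by (1 − r²). Estimating k covariate terms with 40 patients raises the expected variance by 37/(37 − k) and leaves 38 − k df. So V = (1 − r²) × 37/(37 − k). For example, k = 2 and r = 0.5 gives 0.75 × 37/35 = 0.793. The SE ratio is then 0.890, and the detectable difference on 36 df is 0.81 SD.

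| r (r²) | Two terms | Three terms |
|---|---|---|
| 0.3 (0.09) | 0.89 SD | 0.91 SD |
| 0.5 (0.25) | 0.81 SD | 0.82 SD |
| 0.7 (0.49) | 0.67 SD | 0.68 SD |

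With two terms, power for 0.8 SD becomes 71%, 79% and 92%. At r = 0.5 the equivalent unadjusted size is 20/0.793 = 25 per arm.

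**5. Break-even.** V = 1 when r² = k/37, which is 0.05 for two terms and 0.08 for three. Below that, adjustment does not reduce the expected variance.

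**The case against.** The strongest reply is that the unadjusted comparison of randomised arms is valid. This is right and sets the limit of the point. A reader might infer from the mixed levels and missing stratification that the trial result will be biased or its error rate inflated. The documents do not support that: over all randomisations the test keeps its level. Only the result conditional on a particular imbalance is affected, and no baseline table is given to show one.

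A reader might also infer a sure gain in precision. The documents report no correlation of any covariate with any outcome, and nowhere say that level predicts pain, narcotic use or stay. The Background sentence on pain control concerns chronic amputation pain and not inpatient outcomes, and it does not mention opioid use. At r = 0.3, three terms buy nothing.

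Nor is adjustment the only route left to more precision. Pain was scored daily until discharge and followed for six months, so repeated scores could be averaged or modelled.

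Saying flatly that level was never recorded would go too far. The data list is introduced as what was included, and the follow-up sentence mentions unspecified further data. Even if level was captured, no planned analysis uses it.

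Feasibility is partly inference. Of the retrospective patients the protocol says "These patients will be identified through an Epic report"; it does not say the report covers the 40 trial patients or holds preoperative opioid use. Level should be recoverable, because the operation itself defines it. Opioid history is much less certain.

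**Conclusion.** The point stands as a recommended improvement. The randomised comparison has about 20 per arm, mixed amputation levels, no stated stratification and only unadjusted tests. Level and preoperative opioid use are not among the listed variables, and the collected age and ASA class are not used for adjustment. What is lost is some precision and protection against whatever imbalance actually occurred.

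An imbalance of 20 points or more in level has probability 23% to 27%, or 30% to 34% with the total fixed, if 30% to 50% are above-knee. The gain in detectable difference runs from almost nothing to about a quarter: from 0.91 SD to between 0.89 and 0.67 SD with two terms, for correlations of 0.3 to 0.7. All of these figures rest on the assumptions listed above.

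**What to change.** Before the trial data are analysed by arm:

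- Take amputation level from the operative record for the 40 trial patients and for the retrospective cohort. In the cohort (about 1000 − 40 = 960 patients, not randomised) the same omission is a confounding problem, so one extraction serves both parts.
- State a separate analysis for the trial: a linear model by randomised arm, with narcotic use and stay on the log scale, adjusted for level and ASA class. Enter ASA class as a single term to save degrees of freedom. Keep the unadjusted test as sensitivity.
- Add preoperative opioid use as a third term only if it can be extracted completely and coded blind to arm. Blinding needs attention because the study coordinator both assembled the envelopes and creates the Epic report.
- Do not adjust for length of operation, which is recorded after the block.

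The cost is a short chart extraction, one paragraph of analysis text, and two or three degrees of freedom. If the covariates turn out to be weak predictors, the adjusted analysis will be no more precise than the unadjusted one.
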